2. OBJECTIVES AND ENDPOINTS

This Phase IIa, multicenter, randomized, double-blind, placebo-controlled, crossover study will evaluate the efficacy, safety, pharmacokinetics, and pharmacodynamic (PD) effects of GDC-6599 compared with placebo in patients with a history of chronic cough. It will assess the potential benefit of GDC-6599 to reduce cough frequency and severity in patients with a diagnosis of CRC with asthma, UCC, or CRC with COPD. The study will also *explore the effects* of GDC-6599 on mannitol-induced cough and/or AHR and the value of mannitol-induced cough hypersensitivity and/or AHR as a prognostic tool in patients with CRC with asthma, UCC, or CRC with COPD as a measure of TRPA1 airway activity. Specific objectives and corresponding endpoints for the study are outlined in [Table 1](#) below.

Table 1 Objectives and Corresponding Endpoints

Primary Objective	Corresponding Endpoint
• To evaluate the efficacy of GDC-6599, as compared with placebo, in patients with CRC with asthma or UCC	• Change in cough frequency per hour, assessed objectively over 24 hours (24-hour OCC) using VitaloJAK® cough recorder, from baseline to Day 14
Secondary Objective	Corresponding Endpoints
• To evaluate the efficacy of GDC-6599, as compared with placebo, in patients with CRC with asthma or UCC	• Change in the severity of cough, as assessed through the use of the patient-reported cough severity VAS and NRS scores, from baseline to Day 14
Safety Objective	Corresponding Endpoints
• To evaluate the safety of GDC-6599 compared with placebo	• Incidence and severity of adverse events, with severity determined according to the DAIDS toxicity grading scale ^a • Change from baseline in targeted vital signs • Change from baseline in targeted clinical laboratory test results
Pharmacokinetic Objective	Corresponding Endpoints
• To characterize the PK profile of GDC-6599	• Plasma concentration of GDC-6599 at specified timepoints
Exploratory Objectives	Corresponding Endpoints
• To evaluate mannitol-induced cough response as a measure of TRPA1 airway activity and treatment benefit of GDC-6599, as compared with placebo, in patients with CRC with asthma or UCC	• Change in cough hypersensitivity to mannitol, measured as the CDR to mannitol, from baseline to Day 14

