4.5.12.1 Data Collection Methods for Clinical Outcome Assessments

The [REDACTED], and VAS will be self-administered at the clinic at specified timepoints during the study (see schedule of activities in [Appendix 1](#)). The NRS and VAS will be self-administered at home via ePRO on a daily basis according to the schedule of assessments. At the clinic, PRO assessments will be administered before the patient receives any information on disease status, prior to the performance of non-PRO assessments, and prior to the administration of study treatment unless otherwise specified.

PRO instruments, translated into the local language as appropriate, will be completed through use of an electronic device provided by the Sponsor (note that [REDACTED] will be completed on paper with responses captured in the ePRO database). The device will be pre-programmed to enable the appropriate instruments to be administered in the correct order at each specified timepoint. The electronic device and instructions for completing the instruments electronically will be provided by the site staff. The data will be transmitted to a centralized database maintained by the electronic device vendor. The data will be available for access by appropriate study personnel.

Patients should be given the following instructions for completing PRO instruments at home:

[figure not shown]
- Patients should complete the instruments in a quiet area with minimal distractions and disruptions.
- Patients should answer questions to the best of their ability; there are no right or wrong answers.

- Patients should not obtain advice or help from others (e.g., family members or friends) when completing the instruments.

During clinic visits, PRO instruments should be administered as outlined below:

- Patients' health status should not be discussed prior to administration of the instruments.
- Sites must administer the official version of each instrument, as provided by the Sponsor. Instruments must not be copied from the protocol.
- Sites should allow sufficient time for patients to complete the instruments, estimated to be 10 minutes at each specified visit.
- Sites should administer the instruments in a quiet area with minimal distractions and disruptions.
- Patients should be instructed to answer questions to the best of their ability; there are no right or wrong answers.
- Site staff should not interpret or explain questions, but may read questions verbatim upon request.

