4.5.12.2 Description of Clinical Outcome Assessment Instruments

Visual Analog Scale

The VAS is a single-item rating used for the subjective assessment of cough severity. Patients will be asked to indicate the severity of their cough by marking a line on a scale between anchor statements of 'no cough' and 'worst cough' using a recall period of 'today'. A copy of the VAS is provided in [Appendix 6](#).

Numeric Response Scale

The NRS is a single-item measure of cough severity. Patients will be asked to rate the severity of their cough from 0 (no cough) to 10 (worst cough) using a recall period of 'today'. A copy of the NRS is provided in [Appendix 7](#).

4.5.13 Blood Samples for Whole Genome Sequencing or Whole Exome Sequencing (Patients at Participating Sites)

At participating sites, blood samples will be collected for DNA extraction to enable WGS or WES to identify variants that are predictive of response to study drug, are associated with progression to a more severe disease state, are associated with susceptibility to developing adverse events, can lead to improved adverse event monitoring or investigation, or can increase the knowledge and understanding of disease biology and drug safety. Research will include exploration of germline variants. The samples may be sent to one or more laboratories for analysis.

Collection and submission of blood samples for WGS or WES is contingent upon the review and approval of the exploratory research by each site's Institutional Review Board or Ethics Committee (IRB/EC) and, if applicable, an appropriate regulatory body. If a site has not been granted approval for WGS or WES, this section of the protocol (Section [4.5.13](#)) will not be applicable at that site.

Genomics is increasingly informing researcher's understanding of disease pathobiology. WGS and WES provide a comprehensive characterization of the genome and exome, respectively, and, along with clinical data collected in this study, may increase the opportunity for developing new therapeutic approaches or new methods for monitoring efficacy and safety or predicting which patients are more likely to respond to a drug or develop adverse events. Data will be analyzed in the context of this study but may also be explored in aggregate with data from other studies. The availability of a larger dataset will assist in identification and characterization of important biomarkers and pathways to support future drug development.

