For sampling procedures, storage conditions, and shipment instructions, see the laboratory manual.

Blood samples collected for WGS or WES are to be stored until they are no longer needed or until they are exhausted. However, the storage period will be in accordance with the IRB/EC-approved Informed Consent Form and applicable laws (e.g., health authority requirements).

Refer to Section 4.5.10 for details on use of samples after patient withdrawal and confidentiality standards for data.

Data generated from blood samples collected for WGS or WES will be analyzed in aggregate rather than on an individual patient basis. Thus, there will be no identification and reporting of incidental findings to investigators or patients.

If permitted by local law, a patient may request access to uninterpreted WGS or WES data derived from analysis of his or her blood sample. If a patient wishes to access these data, the investigator must inform the Sponsor, using the following email address: [contact]. The Sponsor will provide available data to the investigator in the form of a raw genomic sequencing data file, but will not provide any interpretation of the data. The investigator should not include the data file in the patient's medical record. Samples may be stored and analyzed in the future, and some samples may never be analyzed. Thus, data may not be available at the time of the request or may never be available.

The aggregate results of any conducted research will be available in accordance with the effective Sponsor policy on study data publication.

4.5.14 *Optional Mannitol Challenge Tests*

Consenting patients will undergo optional mannitol challenge tests during each treatment period at Study Visits 4 and 7. Each mannitol challenge test is to be performed at least 2.5 hours after study drug administration. Details on the mannitol challenge test are provided in Section 4.5.5 and in the mannitol challenge test guidance. See Section 4.5.6 for details on cough monitoring during the challenges. Medication restrictions prior to the mannitol challenge are provided in Section 4.4.4.

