Appendix 1: Schedule of Activities for Part A and Part B

- j Test for FSH may be performed at screening to confirm postmenopausal state, if required per local guidelines.
- k All women of childbearing potential will have a serum pregnancy test at screening. Urine pregnancy tests will be performed at specified subsequent visits. If a urine pregnancy test is positive, it must be confirmed by a serum pregnancy test. On days when both pregnancy test and study drug administration are scheduled, the pregnancy test results must be available prior to dosing.
- l [REDACTED]
- m Urine sample for urinalysis only. Leftover urine sample should not be collected for urine creatinine or biomarkers.
- n COVID-19 testing to be performed as per local regulations or institutional policies.
- o Chest X-ray is to be performed in the following instances:
 - Patients with CRC with asthma or UCC: if no scans have been completed within the last 5 years prior to screening.
 - Patients with CRC with COPD: if no scans have been completed within the last 6 months prior to screening.
- p [REDACTED]
- q On days when multiple PRO assessments are scheduled, the order of questionnaire completion is the following: [REDACTED], VAS, and NRS.
- r VAS will be self-administered once at screening visit via an electronic device at the study site. VAS and NRS will be self-administered daily in the evening during the remainder of screening and treatment periods using a take-home electronic device.
- s The patient is to perform a minimum of three acceptable FVC maneuvers according to the ATS/ERS 2019 guidelines (Graham et al. 2019). The difference between two largest acceptable FVC and FEV₁ measurements must be within 0.15 L (150 mL) variability to meet the repeatability criteria. If there is greater than 0.15 L variability between the three readings, the patient is to perform another FEV₁ measurement. Details on spirometry are provided in Section 4.5.7 and in the pulmonary function and cough monitoring guidance documents. For the screening visits, pre-bronchodilator spirometry should be performed immediately prior to initiating the mannitol challenge test to determine the pre-challenge FEV₁ % predicted value. For subsequent study visits, pre-bronchodilator spirometry should be performed immediately prior to initiating the mannitol challenge test if optional mannitol challenge tests are performed, or should be performed at least 2.5 hours following drug administration.

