Do not reproduce or distribute. The Sponsor will provide sites with all instruments to be completed in this study.

Please mark the line to indicate the severity of your cough during the last 24 hours.

[figure not shown]

Appendix 7

[figure not shown]
Numeric Response Scale

[figure not shown]
Do not reproduce or distribute. The Sponsor will provide sites with all instruments to be completed in this study.

[figure not shown]
Please rate the severity of your cough during the last 24 hours.

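### In patients who take the optional mannitol challenge at Visit 4 or 7, that evening's VAS/NRS rating covers the challenge, so the Day 14 secondary endpoint mixes provoked with spontaneous cough

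*Combined protocol and SAP*

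**What the plan says.** Table 1 (Section 2) gives the secondary endpoint as: "Change in the severity of cough, as assessed through the use of the patient-reported cough severity VAS and NRS scores, from baseline to Day 14".

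Footnote r of Appendix 1 sets the time of rating: "VAS and NRS will be self-administered daily in the evening during the remainder of screening and treatment periods", on a take-home device. The only clinic rating that the footnote names is at screening: "VAS will be self-administered once at screening visit via an electronic device at the study site". The schedule adds ratings at safety follow-up and treatment discontinuation, but no separate clinic VAS or NRS at Visit 4 or 7.

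The recall period is given in two ways. Section 4.5.12.2 uses today for both scales. The instrument in Appendix 6 reads "Please mark the line to indicate the severity of your cough during the last 24 hours", and Appendix 7 has the same window for the NRS.

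On the challenge, Section 4.5.14 says: "Consenting patients will undergo optional mannitol challenge tests during each treatment period at Study Visits 4 and 7". Section 4.3.2 places those visits on Days 14 and 43. Footnote t requires at least 2.5 hours between study drug and challenge, and refers to Visit 4 and/or 7. Section 4.5.5 requires a challenge at Visit 1; none is scheduled at Visits 2 or 5.

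**The concern.** A severity rating meant to describe the patient's own cough is taken a few hours after a procedure that makes the patient cough. Every participant was selected for that response, since entry requires at least 12 coughs per 100 mg of mannitol (Section 4.1.1.1).

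The protocol separates the challenge from the objective measure: footnote y starts the VitaloJAK recording at the end of the test. The diary has no such rule. Section 4.5.12.1 does put clinic questionnaires "prior to the performance of non-PRO assessments, and prior to the administration of study treatment unless otherwise specified", but that governs ratings made at the clinic, not the home evening diary.

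What is at stake is the meaning of the estimate. Section 3.3.5 says the study will test whether mannitol-induced cough depends on TRPA1, and change in the coughs-per-dose ratio is an exploratory endpoint. If the drug does reduce provoked cough, part of that effect would appear as a VAS/NRS benefit on everyday cough. Section 6.4 groups data by treatment received in each period and does not mention challenge status.

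**Working it through.** The plan gives no figure of its own to reproduce here: no expected consent share, no VAS variability and no effect size. The check therefore covers timing, baseline and an illustrative size.

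**1. Does the evening rating cover the challenge?** Assume a challenge between 08:00 and 17:00 and a rating between 18:00 and 23:00. The gap runs from 18 − 17 = 1 hour to 23 − 8 = 15 hours. It is always on the same day and under 24 hours, so both recall wordings cover the challenge.

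**2. How much cough does a challenge provoke?** At the entry threshold, coughs = 12 × dose / 100. At the full cumulative 635 mg (Section 4.5.5) this is 76.2. If the test stops early, at an assumed 155 mg, it is 18.6. Neither count converts to VAS points from anything in the documents.

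**3. Is baseline free of it?** Footnote a allows randomization from 7 days into screening, and the screening visit may spread over at most 3 days. The required screening challenge is then at least 7 − 3 = 4 evenings before the last pre-dose evening, so a last-pre-dose baseline is clean. A mean of the last seven evenings would include the challenge evening, with weight 1/7, if screening lasts 7 days. It would not with 10, 14 or 21 days. The protocol does not say which baseline applies. Footnote r also does not name the washout, so the source of a Period 2 pre-dose rating is unclear.

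**4. Shift in change from baseline, within a period.** Let f be the share challenged and d the VAS points that a challenge adds that evening, both assumed. Shift = f × d, with a clean baseline.
- Single evening: 0.25 × 5 = 1.25 points, up to 1.0 × 20 = 20 points.
- Mean of seven evenings including the challenge evening: 1.25 / 7 = 0.18, up to 20 / 7 = 2.9 points.

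**5. Shift in the drug-placebo contrast, both periods challenged.** Shift = f × (d on drug − d on placebo). With f = 0.5 and d on placebo = 10:
- drug leaves mannitol cough unchanged: 0.5 × (10 − 10) = 0;
- drug reduces the shift by a quarter: 0.5 × (7.5 − 10) = −1.25;
- drug halves it: 0.5 × (5 − 10) = −2.5 points, in favour of drug.

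On a seven-evening mean the last figure is −2.5 / 7 = −0.36.

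**6. One period challenged.** That patient's contrast moves by the full d, against the drug if the challenge was in the drug period and in its favour if in the placebo period. In the cohort mean, such patients contribute d × (share challenged on drug only − share challenged on placebo only), taking d as equal on both. Balanced numbers cancel in the mean and add only noise.

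**The case against.** The strongest counter-argument is that the objective is efficacy against placebo in a within-patient crossover. A shift common to both periods drops out, and Section 4.5.14 plans the challenge in both. This stands, and it limits the point. A reader might infer that the 1.25 to 20 points in step 4 is bias in the treatment effect. The documents do not support that: it is a shift in change from baseline, and only the difference between the drug and placebo shifts reaches the contrast.

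A reader might also infer that baseline ratings never contain provoked cough. That is not established either, because baseline is undefined and a challenge is required at screening. Nor is one-period challenge the expected pattern: footnote t is a timing rule whose wording allows it, and no frequency is given.

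Other limits also stand. No document figure links provoked coughs to an evening rating. Even the direction is not assured, because Section 5.1.2.1 provides an inhaled short-acting bronchodilator after a positive challenge, and its effect on the rating is unknown. The analysis is descriptive, the challenge is opt-in, and the primary recording starts after the test. The challenge guidance and the diary programming, which are not part of these documents, may contain relevant instructions.

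A last objection is that the evening before the visit is not fully comparable either. Section 4.4.4 restricts some medicines for up to 72 hours or 4 days before a challenge, so Days 13 and 42 fall within those restrictions. True, but Days 14 and 43 do as well. Moving the rating removes the provoked cough without making this difference worse.

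**Conclusion.** The point holds. Followed as written, the plan puts provoked cough into the Day 14 VAS and NRS of every patient who takes the challenge that day, and nothing in the protocol tells patients to discount it. Within-period change from baseline is distorted in those patients whenever baseline is a pre-dose evening without a challenge.

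For the drug-placebo contrast, the bias is zero if the drug leaves mannitol cough unchanged, and about 2.5 VAS points in favour of drug under one illustrative set of assumptions (50% challenged in both periods, a 10-point shift, halved by the drug). The full shift applies only to a patient challenged in one period. Consent share, shift and drug effect on provoked cough are all assumed, and a multi-evening mean would dilute the result.

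This is a biased estimate of a secondary endpoint in a subset of unknown size. It is not an error-rate problem, since Section 6.4 plans no hypothesis tests, and it does not reach the primary endpoint by this route. As the study's stated purpose is estimation, it should be corrected.

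**What to change.** In Table 1 and footnote r:
- Define the on-treatment VAS/NRS value as the evening rating before Visit 4 and before Visit 7 (Days 13 and 42 on the nominal schedule), or a mean of the last few evenings ending then, for all patients and both periods, challenged or not.
- Define baseline as pre-dose evening ratings that exclude any challenge evening, and state whether Period 2 has its own baseline. If it does, the diary must explicitly cover the evenings before Day 30.
- Report challenge-day ratings descriptively only.
- Reconcile the two recall wordings.

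In Section 6.4, add a summary by challenge status in each period, because medication withholding still differs between challenged and unchallenged patients.

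The cost is a few sentences. The on-treatment evenings are already in the daily diary; only a separate Period 2 baseline might need extra diary evenings. The value reflects one dosing day fewer, and the rating no longer overlaps the Day 14 24-hour cough recording. That overlap was only partial, because the recording starts about 3 hours after the dose, or after the challenge, and runs into the next day.

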Appendix 1: Schedule of Activities for Part A and Part B

- u Post-bronchodilator spirometry replaces the recovery spirometry assessment [*if required*] following mannitol challenge at screening. Post-bronchodilator spirometry should be performed per the pulmonary function and cough monitoring guidance documents at least 1 hour following the mannitol challenge test or on a separate study visit within the screening period before or after the mannitol challenge test.
- v Details on cough monitoring are provided in Section 4.5.6 and in the pulmonary function and cough monitoring guidance documents.
- w Cough monitoring with the VitaloJAK cough recorder will begin on the first day of screening and will continue for 24 hours if the screening visits occur over multiple visits. If screening visit occurs during a single visit, use of the VitaloJAK cough recorder should start at least 30 minutes after the mannitol challenge test.
- x Cough monitoring with the VitaloJAK cough recorder will begin a minimum of 24 hours prior to study drug administration and will conclude on the day of study drug administration.
- y Cough monitoring with the VitaloJAK cough recorder will begin at the *end of the mannitol challenge test* (i.e., immediately after spirometry following the last dose of mannitol or after the final spirometry following the recovery period [*if required*]) and will continue for 24 hours after mannitol challenge recovery period. If the mannitol challenge test is not performed, cough monitoring with the VitaloJAK cough recorder will begin approximately 3 hours after study drug administration.

z [REDACTED]

aa Study drug (GDC-6599 or placebo) will be administered [REDACTED] on Days 1–14 and on Days 30–43. [REDACTED]

bb [REDACTED]

[figure not shown]
cc [REDACTED]

[figure not shown]
dd After informed consent has been obtained but prior to initiation of study drug, only serious adverse events caused by a protocol-mandated intervention should be reported. After initiation of study drug, all adverse events will be reported until 28 days after the final dose of study drug.

[figure not shown]
Reference:

[figure not shown]

[figure not shown]

[figure not shown]

Appendix 6

Visual Analog Scale

Do not reproduce or distribute. The Sponsor will provide sites with all instruments to be completed in this study.

Please mark the line to indicate the severity of your cough during the last 24 hours.

[figure not shown]

Appendix 7

[figure not shown]
Numeric Response Scale

[figure not shown]
Do not reproduce or distribute. The Sponsor will provide sites with all instruments to be completed in this study.

[figure not shown]
Please rate the severity of your cough during the last 24 hours.

